8.1.2.1. Serious Adverse Events

Planned surgeries should not be reported as SAEs unless the underlying medical condition has worsened during the course of the study.

Planned hospitalisations or elective procedures for underlying preexisting conditions that are already recorded in the patient's medical history at the time of study enrolment should not be considered SAEs. Hospitalisation or prolongation of hospitalisation without a precipitating clinical AE (for example, for the administration of study therapy or other protocol-required procedure) should not be considered SAEs.

An SAE is any AE during this study that results in 1 of the following outcomes:

- death
- initial or prolonged inpatient hospitalisation (except for study drug administration)
- a life-threatening experience (that is, immediate risk of dying)
- persistent or significant disability/incapacity

- congenital anomaly/birth defect
- considered significant by the investigator for any other reason

Important medical events that may not result in death, be life-threatening, or require hospitalisation may be considered SAEs when, based on appropriate medical judgement, they may jeopardise the patient and may require medical or surgical intervention to prevent one of the outcomes listed in this definition.

SAEs due to disease progression, including death, should not be reported unless the investigator deems them to be possibly related to the study drug.

Study site personnel must alert Lilly or its designee of any SAE within 24 hours of investigator awareness of the event via a sponsor-approved method. If alerts are issued via telephone, they are to be immediately followed with official notification on study-specific SAE forms. This 24-hour notification requirement refers to the initial SAE information and all follow-up SAE information.

If an investigator becomes aware of SAEs occurring after the patient's participation in the trial has ended, and the investigator believes that the SAE is related to a protocol procedure or study drug, the investigator should report the SAEs to the sponsor, and the SAEs will be entered in the Lilly Safety System.

Recommendations for reporting SAEs may be found in [Attachment 5](#).

Information on SAEs expected in the study population independent of drug exposure and that will be assessed by the sponsor in aggregate periodically during the course of the trial may be found in the IB.

8.1.2.2. Adverse Event and Serious Adverse Event Reporting

Data on SAEs that occur before the end of trial will be stored in the collection database and the Lilly Safety System.

8.1.2.2.1. Prior to Administration of Study Drugs

AE or SAE collection begins after the patient has signed informed consent and has received study drug. If a patient experiences an AE or SAE after signing informed consent but prior to receiving study drug, only AEs and SAEs related to protocol procedures are required to be collected.

8.1.2.2.2. On Therapy

All AEs and SAEs, regardless of relatedness to study drugs or protocol procedures, occurring while the patient is receiving study drug must be reported to Lilly or its designee. A patient is considered to be receiving study drug from the time he/she receives the first dose of study drug to when he/she receives the last dose of study drug.

8.1.2.2.3. Follow-Up Visits

All AEs and SAEs, regardless of relatedness to study drug(s) or protocol procedures, occurring during the safety follow-up visits occurring at approximately 30 and 100 days after last dose of combination treatment must be reported to Lilly or its designee ([Attachment 1](#)).

For the Phase 1b part only, following the safety assessments (which occur after the patient discontinues from study treatment) which mark the end of the follow-up visit, the patient will be discontinued from the study, unless there is an ongoing AE or SAE that is possibly related to study drug or protocol procedures. In this instance, the patient should be followed in subsequent follow-up visits until the event is resolved, the event is no longer considered to be drug-related, the event becomes stable or returns to baseline, a new treatment is initiated for the patient, or the patient dies or is lost to follow-up.

For the Phase 2 part only, following the safety assessments (which occur after the patient discontinues from study treatment) which mark the end of the follow-up visit, the patient will be followed only for survival (overall and 6, 12, and 18 months), unless there is an ongoing AE or SAE that is possibly related to study drug or protocol procedures. In this instance, the patient should be followed in subsequent follow-up visits until the event is resolved, the event is no longer considered to be drug-related, the event becomes stable or returns to baseline, a new treatment is initiated for the patient, or the patient dies or is lost to follow-up.

If it is deemed to be in the best interest of the patient to start a new anticancer treatment prior to the scheduled end of the follow-up visit, the follow-up visit duration may be shortened. In this case, the follow-up assessments should be completed prior to the initiation of the new therapy.

After the follow-up visits, AEs are not required to be reported unless the investigator feels the AEs were related to either study drug, drug delivery system, or a protocol procedure. If an investigator becomes aware of SAEs believed to be related to protocol procedures or study drug, the investigator should report the SAE to the sponsor, and the SAE will be entered in the Lilly Safety System.

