- Clarification was added to Exclusion Criterion 45 to indicate that patients are to be excluded for a history of severe allergy to study drug components
- Clarifications for dose adjustments for galunisertib were added to [Table JBEF.7.1](#) and within [Section 7](#) to align with the additions of the DLT of \geq CTCAE Grade 3 thrombocytopenia with clinically significant bleeding and the 2 Phase 1b dose levels
- Addition of on-study serum pregnancy tests to be conducted predose on Day 1 of every cycle
- Addition of the collection at baseline information on weight change for the previous 3 months and that weight and weight change from baseline would be assessed
- Inclusion on Phase 1b patients in assessment of overall survival (OS)
- Incorporation of additional information on different galunisertib formulations in consideration of the addition of the 50-mg galunisertib dose levels and corresponding 50-mg tablets
- Addition of pharmacokinetic (PK) time-matched electrocardiograms (ECGs)
- Modifications to the schedule of events ([Attachment 1](#)) and the PK and immunogenicity sampling schedule ([Attachment 4](#)) to improve consistency within the protocol and incorporate amendment changes

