5.9.2. Secondary Objectives

The secondary objectives of this study are:

- to characterise the PK of galunisertib and nivolumab when coadministered
- to characterise the immunogenicity of nivolumab when administered in combination with galunisertib
- to estimate the OS rate following the final analysis/evaluation of OS and the landmark OS at 6, 12, and 18 months following the start of therapy with the combination of galunisertib and nivolumab
- Phase 2 only: To assess the preliminary antitumour activity including PFS, ORR, duration of response, and time to response of the combination of galunisertib and nivolumab in patients with NSCLC or HCC

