6.2. Summary of Study Design

This is a Phase 1b/2 study that will be conducted in 2 parts. The first part (Phase 1b) of the study will consist of an open-label, dose-escalation assessment of the safety and tolerability of galunisertib administered at 50 mg QD (Cohort 1), 50 mg BID (Cohort 2), 80 mg BID (Cohort 3), and 150 mg BID (Cohort 4) administered with nivolumab 3 mg/kg Q2W in patients with advanced refractory solid tumours ([Figure JBEF.6.1](#)). The second part (Phase 2) of the study will be disease restricted to include 2 expansion cohorts in patients with recurrent or refractory NSCLC (n = approximately 25 patients) or HCC (n = approximately 25 patients) receiving nivolumab 3 mg/kg Q2W plus galunisertib at the dose determined from the Phase 1b part. Additional expansion of individual cohorts may occur depending upon activity based upon a 2-stage design after 3 cycles. Details are found in [Section 10.1.1](#). NSCLC has a historically good activity under nivolumab monotherapy; HCC has documented activity with galunisertib therapy.

Additional cohorts of patients with specific alternative tumour histologies may be added, but this addition will require an amendment.

Safety assessments including laboratory assessments, PK blood draws, vital sign collection, medical history, weight and at baseline change in weight for previous 3 months, and physical examinations will be performed according to the schedule of events in [Attachment 1](#). AEs will be assessed continuously during the study and for 100 days after the last dose of combination treatment. ECGs will be collected as described in [Attachment 1](#) and [Attachment 4](#). ECHOs will be collected at baseline and every 8 weeks (end of every other cycle). Additionally imaging examinations will be performed approximately every 8 weeks (end of every other cycle).

Efficacy measures will be assessed following every other treatment cycle (end of Cycles 2, 4, etc). Disease assessment with CT and/or MRI, as appropriate, will be performed at baseline and approximately between Days 22 and 28 of every other cycle and completed before the first dose in the next cycle (or approximately every 8 weeks), until disease progression or patient withdrawal from the study.

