Treatment decisions related to patient management and whether to treat a patient with advanced refractory solid tumours with additional cycles of study therapy will be based on RECIST version 1.1 for all study patients except patients with glioblastoma, for whom treatment decisions will be based on RANO criteria.

[figure not shown]
At the sponsor's discretion, scans and measurements may be collected and reviewed by independent radiologists using RECIST version 1.1/RANO criteria at a later date, or at any time during the study.

The planned duration of treatment is not fixed; patients will remain on study treatment until they fulfil 1 of the criteria for study discontinuation ([Section 6.3](#)). Patients demonstrating a benefit from treatment may continue on combination therapy if the patient and investigator feel that the patient is benefiting from treatment. If a patient experiences an AE that requires the patient be discontinued from 1 of the 2 study drugs, the patient should continue on the other study drug

(Section 7.2.4). Landmark analysis of all study patients will occur at 6, 12, and 18 months, and OS will be assessed at the end of trial.

Patients who have discontinued from combination treatment will enter the Safety Follow-Up period with visits at approximately 30 and 100 days. If the patient has only discontinued from 1 of the 2 study drugs, the patient will continue on treatment until they discontinue from the second drug, at which time they will enter the Safety Follow-Up period as noted above. If patients have discontinued treatment for reasons other than disease progression, tumour assessments should continue every 8 weeks until disease progression occurs, initiation of a new anticancer therapy, the patient dies or is lost to follow-up. Patients will be followed for survival approximately every 12 weeks (± 7 days) until death or end of trial. This follow-up may occur through a phone call, email, or visit by the patient or the patient's caretaker.

Refer to [Attachment 1](#) for the study schedule.

Abbreviations: approx = approximately; BID = twice daily; IV = intravenous; HCC = hepatocellular carcinoma; n = number of patients; NSCLC = non-small cell lung cancer; Q2W = every other week; QD = daily; TBD = to be determined.

Figure JBEF.6.1. Study H9H-MC-JBEF design.

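### Protocol 8.1.2.2.3 takes Phase 1b patients off study after the safety follow-up, while the rest of the protocol follows them for survival until death or end of trial

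*Protocol*

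**What the plan says.** Protocol 8.1.2.2.3 places the safety follow-up visits at "approximately 30 and 100 days after last dose of combination treatment". It then gives one paragraph for each part of the study.

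- **Phase 1b only.** The text on the safety assessments reads: "which mark the end of the follow-up visit, the patient will be discontinued from the study, unless there is an ongoing AE or SAE". Only events with a possible link to study drug or procedures count for this exception.
- **Phase 2 only.** After the same assessments, "the patient will be followed only for survival (overall and 6, 12, and 18 months"), with the same exception for ongoing events.

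Elsewhere the current text treats both parts alike:

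- **Protocol 5.9.2** has a secondary objective to estimate OS and "the landmark OS at 6, 12, and 18 months following the start of therapy", with no phase limit. The next bullet does carry one: "Phase 2 only: To assess the preliminary antitumour activity including PFS, ORR". SAP 4.2 repeats both.
- **Protocol 6.2** states: "Landmark analysis of all study patients will occur at 6, 12, and 18 months, and OS will be assessed at the end of trial". It adds survival contact about every 12 weeks until death or end of trial, by phone, email or visit.
- **Protocol 6.2.4** defines Long-Term Follow-Up as running from the day after the 100-day follow-up to death or end of trial, for any patient.
- **Protocol 8.3** lists OS and survival at 6, 12 and 18 months as efficacy measures without restriction.
- **Attachment 1, Phase 1b schedule,** has its own Survival row (at least every 12 weeks until death) and a Long-Term Follow-Up footnote.
- **SAP 6.7.2** plans to list and summarise OS by dose for Phase 1b.

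**The concern.** The two instructions cannot both be carried out. A Phase 1b patient who has finished the safety follow-up with no related event ongoing is off study under 8.1.2.2.3, and in 12-weekly survival follow-up under 6.2, 6.2.4 and Attachment 1. Nothing in the protocol says which prevails.

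What is at stake is OS in Phase 1b. SAP 6.7.1 censors OS at the last contact for patients not known to have died. If a site applied 8.1.2.2.3, censoring would follow treatment discontinuation by a nearly fixed interval. If patients who stop early have a different prognosis from those who continue, which is plausible but not stated in the documents, that censoring is informative and the survival estimates could be biased.

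**Working it through.** There is no design figure to reproduce. The check is a reading of the text, followed by arithmetic on the consequence.

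**Can the sentence be read harmlessly?** One could take leaving the study to mean only that adverse event visits end, since the sentence sits in a section on event reporting. The parallel Phase 2 paragraph rules this out. The two paragraphs have the same structure and the same exception, and they differ in whether survival follow-up continues. Protocol 6.3.2 also distinguishes stopping study drug from leaving the study.

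**Evidence of intent.** Protocol 5.4 lists the inclusion of Phase 1b patients in the OS assessment among the changes made by amendment (a). That suggests the sentence is a leftover. It is background only, because the contradiction stands on current text.

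**Consequence if 8.1.2.2.3 is followed.** Inputs:
- 28-day cycles, with nivolumab on Days 1 and 15 (protocol 7.2.1)
- last safety visit about 100 days after last dose (8.1.2.2.3)
- scans "approximately between Days 22 and 28 of every other cycle" (6.2)
- one month = 365.25/12 = 30.44 days

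*Early stopper, counted from last dose.* Cycle 2 Day 15 is day 28 + 15 = 43. Exit is at 43 + 100 = day 143, and 143/30.44 = 4.7 months.

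*Early stopper, counted from the decision to stop, as in 6.2.4.* A decision at the end-of-Cycle-2 scan falls on days 28 + 22 = 50 to 28 + 28 = 56. Exit is at about days 150 to 156, or 4.9 to 5.1 months.

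Both fall before the 6-month landmark at 6 × 30.44 = about day 183.

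*Last dose needed to be under observation at each landmark* (landmark day minus 100):

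| Landmark | Day | Last dose on or after | First scheduled nivolumab dose from then |
|---|---|---|---|
| 6 months | 182.6 | about day 83 | day 85 = 3×28 + 1, Cycle 4 Day 1 |
| 12 months | 365.25 | about day 265 | day 267 = 9×28 + 15, Cycle 10 Day 15 |
| 18 months | 547.9 | about day 448 | day 449 = 16×28 + 1, Cycle 17 Day 1 |

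Galunisertib, taken on Days 1 to 14, gives the same cycles. Day 83 (Cycle 3 Day 27) and day 448 (Cycle 16 Day 28) are not dosing days, and day 265 is Cycle 10 Day 13. On the last-dose clock, treatment must therefore reach Cycles 4, 10 and 17. All days are approximate because the 100-day visit is.

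**Exceptions.** Under 8.1.2.2.3, contact ends earlier if follow-up is shortened to start a new anticancer treatment, and later if a related event is ongoing.

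**The case against.** The strongest reply is that sites would probably follow survival anyway. Protocol 6.2.3 tells investigators to keep to the study schedule for all patients until the sponsor says otherwise. Section 6.3.2 sends patients who stop treatment to Attachment 1, and 8.1.2.2.3 itself cites that attachment. This lowers the likelihood of harm. It does not remove the conflict: 8.1.2.2.3 is the phase-specific rule for what happens after these visits, and a site obeying it would be complying with current text.

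Second, the SAP asks little of Phase 1b survival. Section 6.7.2 plans only listing and summary by dose there. Kaplan-Meier curves, medians and optional rates at 6, 12 and 18 months are under Phase 2. This narrows the likely damage to incomplete descriptive OS in dose groups of 3 to about 15 evaluable patients. Even so, protocol 5.9.2 and 6.2 do call for landmark OS in all patients, and protocol 10.7 brings matching dose-escalation patients into the efficacy presentations.

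Third, the cycle thresholds hold on the last-dose clock only. Counted from the decision to stop, day 83 or day 448 can be reached without entering Cycle 4 or 17. Deaths before exit are still recorded, so only survivors are affected. Both points are correct and leave the conclusion unchanged.

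**Conclusion.** The contradiction is real and lies in current protocol text. Most of the protocol supports survival follow-up for Phase 1b, and the sentence in 8.1.2.2.3 is the exception.

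The harm is conditional on a site acting on that sentence. The rule could then reach any of the 12 to about 60 evaluable Phase 1b patients (Table JBEF.6.1) who are alive at the end of safety follow-up. The number actually lost cannot be estimated from the documents. Bias, as opposed to lost information, further assumes that stopping treatment is related to prognosis.

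OS is a secondary objective, and the primary assessment of dose-limiting toxicity and safety is untouched. The text should be corrected, but this does not threaten the main purpose of the study.

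**What to change.** In protocol 8.1.2.2.3, replace the Phase 1b instruction to take the patient off study with survival follow-up approximately every 12 weeks until death or end of trial, matching 6.2, 6.2.4 and Attachment 1. Keep the provision for ongoing, possibly related events as it stands.

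The cost is one sentence, carried in a protocol amendment with the usual ethics review. It adds no visits or procedures, since the contact is already in 6.2 and the Phase 1b schedule. The change is best made while patients are still being followed, because survival contacts that are missed may not be fully recoverable later.

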6.2.4. Definitions of Study Periods

Terms used to describe the periods during the study are defined below:

- **Baseline or screening (= patient entering the study):** begins when the ICF is signed and ends at the first study treatment (or at discontinuation, if no treatment is given).
- **Study Treatment Period:** begins at the first study treatment (= **patient is enrolled in the study**) and ends on the date the decision to discontinue the patient from combination treatment or if the patient has previously discontinued from 1 or the 2 study drug, ends on the date the decision to discontinue the patient from remaining study drug.
- **Safety Follow-Up:** begins the day after the patient and the investigator agree that the patient will no longer continue combination treatment and includes 30-day and 100-day visits.
 - **30-Day Follow-Up** begins the day after the patient and the investigator agree that the patient will no longer continue study treatment and lasts approximately 30 days.

- **100-Day Follow-Up** begins the day after the 30-day follow-up visit and lasts approximately 70 days or approximately 100 days after the patient is no longer receiving study treatment.
- **Long-Term Follow-Up** begins the day after 100-day follow-up is completed and continues until the patient's death or end of trial (approximately every 12 weeks \pm 7 days the patient will be contacted).
- **Study Completion:** occurs (that is, the scientific evaluation will be complete) following the final analysis/evaluation of OS.
- **End of Trial:** The term "end of trial" refers to the date of the last visit or last scheduled procedure for the last patient (includes follow-up periods). The end of trial occurs after study completion, and after the last patient has discontinued study treatment and completed the 100-day follow-up (if applicable).

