axis of at least 15 mm). Any new lesion considered nonmeasurable at the time of initial progression may become measurable and therefore included in the tumour burden volume if the longest diameter increases to at least 10 mm (except for pathological lymph nodes which must have a short axis of at least 15 mm).

Global deterioration of health status requiring discontinuation of treatment without objective evidence of disease progression at that time should be reported as “symptomatic deterioration.” Every effort should be made to document objective progression (ie, radiographic confirmation) even after discontinuation from treatment.

Glioblastoma Patients

Standard treatment for glioblastomas (including radiation therapy and temozolomide) may result in a transient increase in tumour enhancement (pseudoprogression) in a subset of patients that eventually subsides without any change in therapy. Pseudoprogression may be difficult to differentiate from true tumour progression and may have important implications for patient management. In order to minimise premature discontinuation of study medication and distinguish pseudoprogression from PD, patients initially meeting radiologic criteria for disease progression may continue receiving study medication until confirmation of progression with an MRI performed approximately 12 weeks later.

In order to continue study treatment after assessment of initial radiological progression, the following criteria must be met:

- 1) The patient is believed to demonstrate clinical benefit as determined by the investigator.
- 2) The patient is tolerating study medication.

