8.3. Efficacy Evaluations

The following efficacy measures will be determined:

- ORR and best overall response, time to response, duration of response, and PFS
 - using RECIST version 1.1 ([Attachment 8](#)) for patients with NSCLC, HCC, and tumours other than glioblastoma
 - using RANO (see [Attachment 9](#)) for patients with glioblastoma
- survival at 6, 12, and 18 months following the start of treatment
- OS determined from the date of first treatment until death due to any cause
- change in ECOG performance status

Efficacy measures will be assessed as noted in [Attachment 1](#). Disease assessment with CT and/or MRI, as appropriate, will be performed at baseline and every 8 weeks until disease progression per RECIST version 1.1 or until patients withdraw from the study. For patients who are being treated beyond initial progression, these patients should remain on study treatment until the next assessment period. Patients who are treated beyond progression will be evaluated on an 8 (nonglioblastoma patients)- or 12 (glioblastoma patients)-week basis to determine whether they should continue on treatment. The use of MRI is mandatory to determine tumour response when using RANO criteria. Brain imaging should be performed as clinically indicated. At the sponsor's discretion, scans and measurements may be collected and reviewed by independent radiologists using RECIST version 1.1/RANO criteria at a later date, or at any time during the study.

To confirm objective responses, all lesions should be radiologically assessed, and the same radiologic method used for the initial response determination should be repeated at least 4 weeks following the initial observation of an objective response, using the same method that was used at baseline. If a patient is discontinued from the study, repeat radiology assessments may be omitted if clear clinical signs of PD are present.

To facilitate this effort the radiologist reading the baseline imaging study is asked to provide in the baseline report or in a supplemental report a comparison of the size of target lesions and nodes reported in the baseline study with the size of these same lesions and nodes, if present, in the reference study. The report should also make note of the date of the preceding referenced study. Reference study data provided in the radiologist's report should be entered into the eCRF by the investigator's staff.

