Serum chemistry	X		X		X		X		X		X		X	X	See Attachment 2 .	
HBV DNA	X		X		X		X		X						All patients to be tested. Peripheral blood. Predose	
HCV RNA	X		X		X		X		X						All patients to be tested. Peripheral blood. Predose	
HCC antiviral activity									X						HCC patients only: peripheral blood collection for assessment of qHBsAg. Predose Day 1 at every other cycle (Cycles, 3, 5, n)	
CTCAE v 4.03 grading	X		X		X		X		X		X		X	X	X	Refer to Section 8.1.2.4 for reporting guidelines.
Concomitant meds	X		X		X		X		X		X		X	X	X	Throughout study as needed
ECOG performance Status	X				X				X				X	X		
PK sampling	X	D 14	X		X	D 14	X		C4 only							See Attachment 4 for timing.
Tumour measurement (palpable or visible)								X				X	X		To occur on or between Days 22 to 28 of every other cycle. At long-term FUP, every 12 weeks as appropriate.	
Radiological tumour assessment								X				X	X		MRI/CT scan. These scans can be performed locally and transmitted to a central imaging vendor. To occur on or between Days 22 to 28 of every other cycle. At short-term FUP, every 8 weeks as appropriate.	
Radiological tumour assessment for treatment past initial progression															MRI/CT scan. These scans can be performed locally and transmitted to a central imaging vendor. For patients who are being treated beyond initial progression, these patients should remain on study treatment until the next assessment period. Patients who are treated beyond progression will be evaluated on an 8-week basis to determine if they should continue on treatment.	
Survival													X		At FUP, at least every 12 weeks until death.	
Immunogenicity	X	D 14	X		X				*					X	Window of ±7 days for 100-day FUP. * Collected at Week 13 and every 16 weeks thereafter (ie, Week 29, 45, etc.)	

During and Post-Study Assessments—Phase 2 Dose Expansion

		Cycle 1				Cycle 2				Cycle 3-n				Follow-Up (days)			Comments
Relative Week Within a Cycle		1	2	3	4	1	2	3	4	1	2	3	4				
Relative Day Within a Cycle^a		1	8	15	22	1	8	15	22	1	8	15	22	Short-term		Long-term ^c	
														30 ^b	100		
Bio-marker samples	Tumour biopsy			1/2		1/2											Required, with half of patients randomly assign to biopsies on either Cycle 1 D15 or Cycle 2 Day 1 post nivolumab dosing.
	Blood Bio-marker sample	D1 & D2	X	X		X		X		C4 only				X			See Attachment 4 for sampling times.

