Progression-free survival (PFS) is defined as the time from the date of first study treatment to the first date of documented progression or death due to any cause, whichever occurs first. For patients who are not known to have died or progressed as of the cut-off date, PFS time will be censored at the date of the last progression-free disease assessment prior to the date of any subsequent anticancer therapy.

Overall Survival (OS) is defined as the time from the date of first study treatment to the date of death from any cause. For each patient who is not known to have died as of the cut-off date, OS will be censored for that analysis at the date of last contact prior to the data inclusion cutoff date (contacts considered in the determination of last contact date include AE date, lesion assessment date, visit date, and last known alive date).

The detailed algorithm for the censoring rules will be described in the analysis dataset requirements (Adam requirements).

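### Protocol 8.1.2.2.3 limits Phase 2 follow-up to survival after about 100 days, contradicting the 8-weekly tumour assessments in 6.2, 8.3 and 7.2.5; where a site follows it, PFS and duration of response can be mis-measured

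*Protocol*

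**What the plan says.** Three protocol sections keep tumour assessment going after treatment stops:

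- Section 6.2, for patients who stop for a reason other than progression: "tumour assessments should continue every 8 weeks until disease progression occurs, initiation of a new anticancer therapy", death or loss to follow-up. It sets no time limit.
- Section 8.3, for disease assessment in general: "every 8 weeks until disease progression per RECIST version 1.1 or until patients withdraw from the study".
- Section 7.2.5, on patients taken off treatment for symptomatic deterioration: "Every effort should be made to document objective progression (ie, radiographic confirmation) even after discontinuation from treatment".

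One section points the other way. Section 8.1.2.2.3 states that after the safety follow-up, in Phase 2, "the patient will be followed only for survival (overall and 6, 12, and 18 months". Its only exception is an ongoing adverse event possibly related to study drug or procedures. It makes none for patients who have not progressed.

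The Phase 2 table in Attachment 1 sits between the two. The comment on radiological assessment reads "At short-term FUP, every 8 weeks as appropriate" and gives no frequency for long-term follow-up, which under Section 6.2.4 "begins the day after 100-day follow-up is completed". The only tumour instruction for the long term is in the row for palpable or visible lesions: "At long-term FUP, every 12 weeks as appropriate". That is not imaging.

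SAP 6.7.1 takes as the PFS event the "first date of documented progression or death due to any cause, whichever occurs first". Duration of response likewise ends at progression or death. Patients not known to have progressed or died are censored at the last assessment before any subsequent anticancer therapy (for duration of response, systemic therapy). The detailed censoring algorithm is left to the dataset requirements.

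**The concern.** A site has two incompatible instructions for a Phase 2 patient who comes off both drugs without progression and is still progression-free when the safety follow-up ends. The documents do not say which prevails. If the site follows 8.1.2.2.3, imaging ends while vital status is still collected, and Section 6.2 allows that contact to be by phone or email.

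The SAP rules then misplace the outcome in one of two ways. If the patient progresses unseen and later dies, the event is dated at death and the unscanned interval counts as progression-free time. If the patient is alive at the cut-off, follow-up is cut back to the last scan. The visible SAP text has no rule for a death after a long gap without assessments.

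PFS and duration of response are Phase 2 secondary endpoints (Protocol 5.9.2), and SAP 6.7.2 allows rates at 6, 12 and 18 months. Their values could then depend partly on which section a site used, and a scan not done cannot be recovered at analysis.

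**Working it through.** The plan states no figure on this point, so there is nothing to reproduce. The check has four steps.

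**1. Scans that fit into the safety follow-up.** Inputs: 100 days (6.2.4) and an 8-week interval, 56 days (6.2). 100 / 56 = 1.8. If the first scan after stopping falls 1 to 44 days later, two fit; if it falls 45 to 56 days later, one fits. The count is therefore 1 or 2.

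**2. One patient (a chosen illustration).** Treatment stops at month 6, progression occurs at month 12, death at month 24.
- Scans continued as in 6.2: progression is found within 56 / 30.4 = 1.8 months, so PFS is between 12 and 13.8 months.
- Scans stopped at 100 days, patient has died: PFS is 24 months.
- Scans stopped at 100 days, patient alive at the cut-off: 6 × 30.4 + 100 = 282 days. The last scan lies between day 282 − 56 = 226 and day 282, so PFS is censored at 7.4 to 9.3 months.

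**3. Cohort-level PFS (illustrative simulation).** Rule A scans every 8 weeks until progression. Rule B stops scans 100 days after treatment stops and sees only deaths afterwards. Both use the SAP event and censoring rules. These assumptions are not in the documents: exponential times; median time to progression 4 or 8 months; median survival after progression 6 or 9 months; 10%, 20% or 30% of patients assigned to stop early, uniformly over days 28 to 168 and independently of prognosis; cut-off at 24 months. Rule B applies at every site. Five of the twelve scenarios, including both extremes of the 12-month difference:

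| Median time to progression / survival after it (months) | Assigned to stop early | Progression never scanned (all patients) | Of these, counted at death | Mean lateness (months) | 12-month PFS, A to B |
|---|---|---|---|---|---|
| 4 / 6 | 10% | 3.4% | 73% | 5.1 | 14.5% to 15.4% (+0.9) |
| 4 / 6 | 30% | 10.1% | 74% | 5.1 | 14.7% to 17.4% (+2.7) |
| 4 / 9 | 30% | 10.5% | 60% | 5.7 | 14.7% to 17.3% (+2.6) |
| 8 / 6 | 10% | 4.5% | 65% | 4.7 | 38.1% to 38.5% (+0.4) |
| 8 / 9 | 30% | 13.9% | 53% | 5.3 | 38.4% to 39.9% (+1.5) |

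Lateness is the death date minus the date of the 8-weekly scan that would have found the progression. Over all twelve scenarios:
- Median PFS is the same under A and B (5.5 months, or 9.2 months with the longer time to progression).
- 12-month PFS is 0.4 to 2.7 points higher under B.
- 18-month PFS differs by −0.4 to +1.5 points.
- Unscanned progressions make up 3.4% to 13.9% of patients. In a cohort of 25 that is 0.034 × 25 = 0.9 to 0.139 × 25 = 3.5 patients.

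**4. Duration of response.** This was not simulated. Its denominator is responders only. As an illustration, SAP 5.2 extends a cohort when 5 to 8 of the first 25 respond. One or two affected responders would then be between 1/8 = 12.5% and 2/5 = 40% of the data.

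**The case against.** The strongest reply is that 8.1.2.2.3 belongs to the adverse event reporting part of the protocol and its exception concerns adverse events, so it governs safety follow-up, while 6.2, 8.3 and 7.2.5 govern scans. That may well be the intention. The wording is not so limited, though: it says what the patient is followed for and names survival, an efficacy outcome.

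The second reply concerns the schedule. A reader might infer that Attachment 1 itself ends all scans at 100 days. The documents do not support that. The radiology comment is silent on the long term and forbids nothing, and the position of the marks in the table text is too uncertain to rely on. Nor does the schedule implement survival-only follow-up: it has the 12-weekly lesion measurement and appears to carry cardiac markers, toxicity grading and concomitant medication into the long term. So the schedule does not resolve the contradiction, but it does not take the side of 8.1.2.2.3 either.

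The third reply concerns size, and most of it stands:
- A patient who stops one drug for toxicity should continue the other (6.2, 6.3.2), which shrinks the group at risk.
- With 25 patients, a 15% rate has a 95% half-width of 1.96 × √(0.15 × 0.85 / 25) = 14 points, well above the 2.7-point shift.
- Setting 100 days against the 17-month median duration of response that Protocol 5.8 cites for nivolumab would mislead, because treatment length is not fixed and scans continue on treatment.
- Nothing in the documents shows that stopping while in response is typical, or that affected patients would be concentrated among responders.

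**Conclusion.** The contradiction is real, stands in current text and is not resolved elsewhere. It should be corrected. A reader might go further and conclude that PFS and duration of response are mis-measured in this trial. The documents support only that they can be: the error needs a site that follows 8.1.2.2.3 over 6.2, 8.3 and 7.2.5, and a patient who is progression-free and without new therapy when safety follow-up ends.

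For such a patient the error can be many months, in either direction. For cohort PFS it is modest: no change in the median and 0.4 to 2.7 points at 12 months, on assumed inputs and with every site stopping scans. Duration of response is more exposed because few patients contribute, but the size is not established. ORR, OS and the primary safety objective of Phase 2 are largely unaffected. The deferred censoring algorithm might handle late deaths differently, but it could not supply a missing progression date.

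**What to change.** Reconcile Protocol 6.2, 8.1.2.2.3, 8.3 and Attachment 1:

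- In the Phase 2 paragraph of 8.1.2.2.3, state that the limit applies to safety follow-up, and that patients without progression or new anticancer therapy continue the 8-weekly radiological assessments already required by 6.2.
- In the Phase 2 table of Attachment 1, extend the radiological assessment row to long-term follow-up under the same condition, and align the 12-weekly row for palpable or visible lesions with it.
- Reconcile the parallel Phase 1b sentence in 8.1.2.2.3, which takes patients off the study after the safety visits, with the continued assessments in 6.2.

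The cost is protocol wording and schedule edits, plus a few scans that sites following 8.1.2.2.3 would have skipped. Because 6.2 already asks for them, the change adds no new requirement.
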